10.1 IRB Review and Communications

This protocol, the parental permission, and child assent forms must be reviewed and approved by each clinical center’s IRB before the study begins at that site. In addition, the Data Coordinating Center (DCC) must have

documentation of current IRB approval at all times during the study. The Data Coordinating Center must also have a copy of the informed permission and child assent forms that were approved by the IRB for each clinical center before enrollment will be permitted at the clinical center.

10.2 Informed Consent

10.2.1 Parental Permission

This protocol requires that parents or other legally empowered guardians sign a parental permission form. The parent or legal guardian will be informed about the objectives of the study and the potential risks.

10.2.2 Child Assent

Subjects who are eligible for THAPCA are comatose, and child assent will not be possible at the time of study enrollment. However, during follow up after discharge from the PICU, issues about assent become applicable. Children who are capable of giving assent and who are alert and competent, will be asked, following an age-appropriate discussion of risks and benefits, to give assent to the study for collection of follow up information. Assent will be waived if the child is too young, has a severely reduced mental age, decreased level of consciousness, psychological problems, or other legitimate reasons as judged by the Institutional Review Board at each site.

10.2.3 Subject Consent

Subjects who are eligible for THAPCA are comatose and under 18 years of age. If a subject attains the age of 18 years during the study intervention period, it will not be possible to obtain informed consent from the subject. During the follow up after discharge from the PICU, 18 year old subjects who are alert and competent and capable of giving consent will be asked, following an appropriate discussion of risks and benefits, to give consent to the study for collection of follow up information. Subject consent will be waived if the subject has a severely reduced mental age, decreased level of consciousness, psychological problems, or other legitimate reasons as judged by the Institutional Review Board at each site.

10.3 Risks and Benefits

Potential complications of hypothermia are addressed in the next two sections (Sections [10.4.1 on the next page](#) and [10.4.2 on page 68](#)). The potential

benefit of the intervention (hypothermia) is that it may improve overall survival, and may result in improved neurobehavioral outcome after pediatric cardiac arrest. Subjects assigned control(normothermia) therapy in this interventional trial may also benefit from having body temperature rigorously controlled in the normal range. In usual practice at most children's hospitals, central temperature is not rigorously monitored and controlled. To minimize the risks of this trial, all subjects will have their temperature controlled by the Blanketrol III cooling unit and appropriately-sized Maxi-Therm Lite mattresses.

10.4 Risk of Surviving with Worse Neurobehavioral Outcome

It is known that a significant number of children who have sustained cardiac arrest currently survive with neurological injury. It is expected that a significant number of children participating in THAPCA Trials will also survive with neurological injury regardless of whether they receive the actively maintained normothermic control therapy or therapeutic hypothermia. We do not know at this time whether the chance of surviving with brain injury is more likely in the cooled group or the normothermic control group. The informed consent shall reflect this information.

10.4.1 Complications Reported in Previous Studies

Several clinical trials have now been conducted in both newborn and adult populations that observed therapeutic hypothermia to be safe, so we do not expect clinically important complications associated with hypothermia to be observed in the THAPCA Trials.

Shankaran³⁰ reported an RCT of 205 newborns with birth asphyxia of which 102 were cooled with the Blanketrol II cooling unit for 72 hours. No increased occurrence of cardiac arrhythmia, bleeding, skin changes or death during the cooling period was observed. Additionally, there was no increase in blood stream infection during the hospital course. Other complications that were similar between the hypothermia and control groups were as follows: hypotension, persistent pulmonary hypertension, oliguria/anuria, hepatic dysfunction, disseminated intravascular coagulopathy, hypoglycemia, and hypocalcemia.

The neonatal CoolCap study²⁹ reported elevated glucose in hypothermia group vs control newborns (7.6 vs 5.4 mmol/L), which resolved spontaneously in 24 hours. Scalp edema occurred more commonly in head

cooled patients 32/108 vs. 1/110 controls, and resolved shortly after the end of cooling. There were no major cardiac arrhythmias, venous thrombosis, severe hypotension, or unanticipated serious adverse events reported. Other complications not increased in cooled cases included: hypotension, coagulopathy, prolonged coagulation times, abnormal renal function, hyponatremia, hypokalemia, platelet count less than 100,000/mcl, metabolic acidosis, respiratory distress, systemic infection, hemoconcentration, hypoglycemia, hypocalcemia, and clinical seizures. Liver function elevation was less in cooled cases.

Polderman reported a large adult experience of therapeutic hypothermia with the Blanketrol II cooling unit and mattresses. No increased risk of intracranial hematomas, acute renal failure, clinically significant cardiac complications, pulmonary complications, or deep venous thrombosis were reported.¹⁰⁶ The average duration of cooling was 4.8 days with a range of 1 to 21 days.

Bernard²⁸ reported an adult cardiac arrest RCT in which cooling was done with cold packs and cooling mattresses. No differences in platelet count or WBC during 12 hours of cooling in adult cardiac arrest cases were observed. Potassium levels were observed to be slightly lower at 6 hours in cooled patients compared to normothermic controls (3.6 vs. 4.0 mmol/L; $p=0.06$) and were stable during the period of cooling. On rewarming, potassium levels were greater in cooled patients (4.5 vs 3.9 mmol/L) at 24 hours. Glucose levels were also noted to be higher in cooled patients than normothermic cases (16.2 vs 10.5 mmol/L). The hyperglycemia resolved following rewarming.

10.4.2 Minimizing Risk of Complications in THAPCA Trials

There are several elements of this study design that will help minimize risks to subjects. The exclusion criteria eliminate certain populations that might be at higher risk for complications. These include patients on extremely high pressor infusions, sickle cell anemia, cryoglobulinemia, pregnancy, skin conditions, and patients with Glasgow Coma Score motor scale indicating an ability to localize pain or obey commands. Patients with terminal illnesses or progressive degenerative conditions will also not be eligible for enrollment.

Risk to subjects will also be minimized by the nature of the PICU clinical setting. Patients will be hospitalized in intensive care units and monitored closely for potential complications and adverse events as a part of usual clinical care. Patients will be assessed as per usual clinical care for development of skin injury or excessive cooling which could occur with use of the cooling

blanket. Each clinical site will be instructed to follow the instructions on the Blanketrol III unit and standard of care at their respective institutions. The study investigator will be contacted for central temperatures of 31.0 °C or less. The importance of temperature control will be emphasized in the training session and in the manual of operations. The Blanketrol III unit is equipped with a temperature control safety system that measures and controls the temperature which also will help protect the patient from harm. Temperature control will be implemented in all subjects using the servo-control mechanism available on the Blanketrol III.

We will provide training for clinical investigators and coordinators regarding potential complications of therapeutic hypothermia, study procedures, and the importance of temperature monitoring and maintaining therapeutic temperature ranges. Additional details on potential complications and the appropriate steps to be taken in the event of a complication are outlined below.

Excessive cooling below the therapeutic range. This complication will be treated by increasing the Blanketrol III temperature so that the patient warms to the therapeutic range (32 to 34°C). Excessive cooling below the therapeutic range in the THAPCA Trials could result in life-threatening cardiac arrhythmias. If cooling below the therapeutic range occurs in patients randomized to receive hypothermia, the patient will be rewarmed to the therapeutic range of 32 to 34°C immediately. Arrhythmias will be managed according to standard AHA PALS guidelines. Excessive cooling will be avoided by utilizing two central temperature probes (esophageal and bladder or rectal) and monitoring subject temperature on a continual basis. The temperature of the water in the Blanketrol III will also be monitored and recorded, and temperature control in all subjects will use the servo-control mechanism available with the Blanketrol III. The patient will not be cooled below 32-34 °C therapeutic range. The study investigator will be contacted for central temperatures of 31.0 °C or less. In the event that the temperature difference between central measures is greater than 1.0 °C, the study investigator will be also be notified.

Cardiac arrhythmias. Serious cardiac arrhythmias are not expected to occur unless the temperature falls well below 30 °C. If a clinically significant arrhythmia develops and persists, then the patient would be rewarmed to normal range if determined by the clinical care team to be necessary.

Infection. Infection rates are expected to be high in both groups of subjects (normothermia and hypothermia groups), based on our prior cohort study data of cardiac arrest patients. The clinical team will utilize antibiotics per their usual clinical site practice in the post arrest population. The THAPCA Trials will monitor both hypothermia and normothermia (control) groups for blood stream and urinary infections as outlined in Section 6.3 of the protocol. In the event of a positive culture or suspicion of possible infection, appropriate antibiotics will be initiated based on the clinical care team's hospital experience.

Bleeding. Bleeding will be monitored by measuring the volume per kg of blood products (red blood cells, platelets, fresh frozen plasma, cryoprecipitate) administered during the first seven days. We will also track the number of surgical interventions for bleeding during the first 7 days. Patients with life threatening bleeding or severe coagulopathies will not be eligible for this trial. Life threatening bleeding during the study will be managed per the clinical care team with rewarming to the normal range. Prior TBI studies did not observe bleeding to be more commonly observed in hypothermic patients compared to normothermic patients.

Alterations of Potassium. Initiation of cooling has been associated with slight reduction in potassium serum concentration measurement. Serum potassium levels will be measured at baseline and then at least every 6 hours during cooling and the rewarming period. Rewarming has been associated with mild increase in potassium serum concentration measurement. Therefore, the clinical team will remove potassium from the IV fluids during rewarming and supplement as needed during this period. Thereafter, the clinical care team will measure potassium based on their normal unit practice.

Multiple organ failure and death. Patients who have had cardiac arrests are at high risk for development of multiple organ failure and death. In our previous cohort study, the mortality rate was nearly 50%. Seizures following cardiac arrest varied between 14-26% for in-hospital and out-of-hospital cases. Blood stream infection was also high in the cohort study.

In summary, for the therapeutic hypothermia group of the THAPCA Trials, we do not expect higher rates of adverse effects to be observed based on findings from neonatal and adult RCTs using therapeutic hypothermia for HIE or cardiac arrest.

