1.4 Interventions

Patients will be randomly assigned, in a 1:1 ratio, to receive either therapeutic hypothermia or normothermia (control) therapy within six hours of ROSC/ROC. Therapeutic hypothermia is defined as surface cooling to 32-34 degrees Celsius ($^{\circ}\text{C}$), for a total duration of 48 hours. This will be followed by slow rewarming to a normal temperature (36.0-37.5 $^{\circ}\text{C}$ range) over approximately 16 hours. The control group will have patient temperature maintained within the defined normothermic range (36-37.5 $^{\circ}\text{C}$). Normothermia will be maintained in the control arm during the periods corresponding to cooling, hypothermia, and rewarming of the hypothermia arm. Both study groups will then have temperature maintained in the normal range (36-37.5 $^{\circ}\text{C}$) until 120 hours post ROSC/ROC. Thereafter, temperature will be maintained as is practiced routinely in the clinical center's PICU.

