5.2 Exclusion Criteria

Patients will be ineligible for enrollment if *any* of the following exclusion criteria are met:

- the parent or legal guardian does not speak English or Spanish (the only two languages in which VABS II is standardized)
- randomization is impossible within six hours of ROSC; OR

- patient is on extracorporeal membrane oxygenation (ECMO) when arrest occurs; OR
- continuous infusion of epinephrine or norepinephrine at very high doses ($\geq 2 \mu\text{g}/\text{kg}/\text{minute}$) received immediately prior to randomization; OR
- Glasgow Coma Scale motor response of five (localizing pain or for infants less than two years, withdraws to touch) or six (obeys commands, or for infants, normal spontaneous movement) prior to randomization; OR
- history of a prior cardiac arrest with chest compressions for at least two minutes during the current hospitalization but outside the 6 hour window for randomization; OR
- pre-existing terminal illness with life expectancy < 12 months; OR
- lack of commitment to aggressive intensive care therapies including do not resuscitate orders and other limitations to care; OR
- cardiac arrest was associated with severe brain, thoracic, or abdominal trauma; OR
- active and refractory severe bleeding prior to randomization; OR
- near drowning in ice water with patient core temperature $\leq 32^\circ\text{C}$ on presentation; OR
- patient is pregnant; OR
- patient participation in a concurrent interventional trial whose protocol, in the judgment of the THAPCA investigators, prevents effective application of one or both THAPCA therapeutic treatment arms, or otherwise significantly interferes with carrying out the THAPCA protocol; OR
- patient is newborn with acute birth asphyxia; OR
- patient cared for in a neonatal intensive care unit (NICU) after arrest (ie, would not be admitted to PICU); OR
- patient has sickle cell anemia; OR
- patient known to have pre-existing cryoglobulinemia; OR

- central nervous system tumor with ongoing chemotherapy or radiation therapy; OR
- chronic hypothermia secondary to hypovolemic, pituitary, or related condition for which body temperature is consistently below 37 °C ; OR
- progressive degenerative encephalopathy; OR

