The study interventions will begin in the intensive care unit as soon as possible after informed consent is received. Cardiac arrest patients in the emergency department will be expeditiously transferred to the PICU. Therapeutic hypothermia will not be induced in the emergency department. The setting of the patient's study cardiac arrest (IH vs OH) will be identified, after which the patient will be randomized to a study treatment group (hypothermia or normothermia) in the respective THAPCA Trial (THAPCA-OH or THAPCA-IH). The intervention time period covers the cooling, hypothermia, and rewarming time periods and the interval to 120 hours from the time intervention begins for both arms. Temperature control will be implemented with the Blanketrol III cooling unit (if the Blanketrol III is not available or is already in use, a Blanketrol II can be substituted) and appropriate patient size Maxi-Therm Lite mattresses. Temperature control will use the servo-control mode of the Blanketrol III. The Blanketrol III (and the Blanketrol II) cooling unit and blankets are manufactured by Cincinnati SubZero (CSZ), Cincinnati, OH, in accordance with all applicable Federal regulations. The Blanketrol II has been utilized safely in adult and neonatal clinical trials of therapeutic hypothermia (32 to 34 °C), and the Blanketrol III is the most current model. These prior populations represent the extremes of age ranges for the intended THAPCA Trial (Newborns and Adults vs Pediatric age groups). In prior studies there were no reports of significant skin injury or other complications associated with cooling using

Blanketrol II cooling units.

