7.1 Hypothermia

Patients randomized to receive therapeutic hypothermia (hypothermia group) will have a target temperature of 33 °C plus or minus 1 °C (32 to 34 °C). Hypothermia will be induced using the Blanketrol III cooling unit and Maxi-Therm Lite blankets placed below and over each patient. No internal cooling procedures or devices will be used (e.g., gastric lavage, intravascular cooling catheter). Based on newborn and adult reports that used the Blanketrol II cooling unit, we expect to achieve the target temperature range within 1 to 4 hours of initiating cooling procedures.^{30, 106} For the NICHD Neonatal study, cooling was achieved within 90 minutes³⁰ and in an adult TBI study, 2.8 hours (1.1 to 4.5 hr range) was reported.¹⁰⁶

For patient safety, dual central temperature measurements will be performed. A temperature sensing esophageal probe and temperature sensing Foley catheter (or rectal temperature probe) will be placed for temperature monitoring prior to initiation of cooling. Please note: the esophageal probe is the preferred primary probe which will be connected to the Blanketrol unit. However, in the event that an esophageal probe is not judged to be feasible, the Foley catheter or rectal probe may be used as the primary probe and the remaining probe will be the secondary probe which will be connected to the bedside monitor. For patient safety, the *lowest* value will be assumed correct if there is a discrepancy in measurements. If there is a discrepancy of greater than 2 °C between the two measurements, the temperature probes should be inspected for proper positioning and function. The patient's temperature will be monitored continuously and recorded every 30 minutes until central temperature is 33 °C. If the patient is 33 degree at the time of therapy initiation, the temperature will be monitored every 30 minutes for at least one hour. Thereafter, the temperature will be recorded every hour until rewarming begins.

The hypothermia group will be sedated with midazolam and fentanyl. Other benzodiazepines and narcotics may alternatively be used at the clinical site's discretion. The hypothermia group will be paralyzed with vecuronium until the therapeutic hypothermia temperature range is achieved. Vecuronium for paralysis will be held after the initial cooling period and utilized only as needed for shivering unresponsive to the sedation/analgesia protocol described in Section 7.5 on page 49.

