A potential safety issue exists with hypothermia and insulin use. Serum potassium measurements are known to decrease with therapeutic hypothermia cooling and then increase during the subsequent rewarming period. Insulin is known to significantly decrease serum potassium. If insulin is administered for hyperglycemia associated with hypothermia, it is likely to be associated with worsening of hypokalemia and require additional supplements of large amounts of potassium. On rewarming, this may result in a more exaggerated rise in serum potassium measurement. Therefore, the approach to be recommended for sites in the THAPCA Trials will be to pay special attention to serum potassium and glucose concentrations, and manage glucose, potassium, and insulin administration according to usual clinical practice for each PICU, avoiding extremes of glucose and potassium.

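### The risk section calls severe coagulopathy ineligible but neither exclusion list contains it; secondarily, the 120-hour temperature-control period has two different starting points.

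*Protocol*

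**What the plan says.** **Eligibility.** In the bleeding paragraph of Protocol 10.4.2: "Patients with life threatening bleeding or severe coagulopathies will not be eligible for this trial". Sections 1.3.2 and 5.2 carry the same exclusion list. Its only entry on this subject is "active and refractory severe bleeding prior to randomization". Section 5.3 says that children who satisfy the listed criteria should be offered the trial unless the attending physician objects or the site cannot recruit another patient at that time.

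**End of temperature control.** Section 1.4 keeps both groups in the normal range "until 120 hours post ROSC/ROC", and 6.2 uses the same origin. The introduction to section 7 instead defines the intervention period as covering cooling, hypothermia, rewarming and "the interval to 120 hours from the time intervention begins for both arms". Section 6.1 allows randomisation up to six hours after return of circulation.

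**Two smaller wording differences.**
- Probe disagreement: 10.4.2 has the study investigator told if "the temperature difference between central measures is greater than 1.0" °C. Sections 7.1 and 7.2 use a threshold of 2 °C, above which "the temperature probes should be inspected for proper positioning and function".
- Potassium: 10.4.2 states that "the clinical team will remove potassium from the IV fluids during rewarming", with supplements as needed. Section 7.7 recommends that sites "manage glucose, potassium, and insulin administration according to usual clinical practice for each PICU".

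**The concern.** The protocol describes two different eligible populations. Section 10.4.2 presents non-enrolment of children with severe coagulopathy as one of the ways in which risk is contained. The screening physician works from 5.2, which does not deliver that protection. Section 2.3.3 lists bleeding among the potential adverse effects of hypothermia, and blood product use within 7 days is a safety endpoint (4.4), so the missing criterion bears on a risk that the trial itself monitors. An ethics board reading section 10 would believe that a safeguard exists which the operating criteria lack.

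The 120-hour origin matters less. It fixes when protocol temperature control hands over to usual unit practice, and which laboratory values fall in the recording window of 6.3. With two origins in the text, two sites could each follow the protocol and stop at different times.

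**Working it through.** No sample size, power or alpha is involved. The check is a comparison of sections, with simple arithmetic for the clock.

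**1. Is there a coagulopathy criterion anywhere in the operating text?**

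| Place | What it provides |
|---|---|
| 10.4.2, bleeding paragraph | Life-threatening bleeding or severe coagulopathy: not eligible |
| 1.3.2 and 5.2 | Active, refractory severe bleeding only |
| 10.4.2, opening paragraph | Names risk-reducing exclusions (high-dose pressors, sickle cell anaemia, cryoglobulinaemia, pregnancy, skin conditions, motor score); coagulopathy is not among them |
| 5.3 | Offer to all who meet the criteria; two exceptions, neither about clotting |
| 8.2 | Coagulation parameters collected in patients already enrolled and randomised |

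The bleeding half of the 10.4.2 sentence broadly matches the exclusion list. The coagulopathy half has no counterpart. No coagulation test is described as part of screening, and the baseline coagulation values come too late to act as a filter. A child with severe coagulopathy and no active refractory bleeding passes 5.2 and fails 10.4.2.

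**2. How far apart are the two 120-hour end points?**

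Let *r* be the hours from return of circulation to randomisation (0 to 6, section 6.1), and *d* the hours from randomisation to the start of the intervention (0 or more; the protocol sets no maximum). Measured from return of circulation:

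- end under 1.4 and 6.2 = 120
- end under section 7 = *r* + *d* + 120
- gap = *r* + *d*

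With *r* = 6 and *d* = 0, the ends are 120 and 126 hours, a gap of 6 hours, or 6/120 = 5% of the period. Any start delay adds to this hour for hour. Section 7.1 also equates 120 hours with the end of day 5. If the calendar-day definition given for cultures in 6.3 (Day 1 is the first full day after randomisation) were applied there, the end would fall 120 to 144 hours after randomisation. That is only a possible further reading, but one stated origin would remove it.

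**3. Probe disagreement.** The 1.0 °C figure goes with notifying the investigator, and the 2 °C figure with inspecting the probes. Sections 7.1 and 7.2 also have a rule for any disagreement: take the lower reading in the hypothermia arm and the higher in the normothermia arm. A site can do all of this at once. What is missing is the notification step in section 7, so differences above 1.0 and up to 2 °C prompt a call under 10.4.2 but not under 7.1 or 7.2.

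**4. Potassium.** Section 10.4.2 gives a specific instruction for fluids during rewarming. Section 7.7 gives a general recommendation, which also asks for special attention to potassium and for extremes to be avoided. The six-hourly measurement in 10.4.2 agrees with 6.3 for active cooling and rewarming. The difference is between a directive and a statement of usual practice.

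**The case against.** The best defence on eligibility is that the sentence in 10.4.2 loosely paraphrases the bleeding exclusion, and that an attending physician may decline to have a child approached (5.3). The first part fails because the sentence names coagulopathy as an alternative to bleeding, and a clotting disorder need not come with active refractory bleeding. The second part is individual discretion, not a criterion, and cannot make good a statement that such patients are ineligible.

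On the clock, it is fair to say that 6.2 refers readers to section 7 for detail, that section 7 applies its origin to both arms, and that the gap falls at the end of the normothermia phase, after cooling and rewarming are over. This limits the consequence but does not remove the contradiction.

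A reader might infer more than the text supports:

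- *That the two probe thresholds contradict each other.* They attach to different actions, and both can be followed.
- *That the potassium safeguard is absent from section 7.* Section 7.7 warns of the rise in potassium on rewarming and asks sites to avoid extremes. The wording is in tension, but the safeguard is not missing.
- *That the rewarming rate in 7.1 is inconsistent with its duration.* From the 33 °C target to 36.0 °C at 0.7 °C per 4 hours takes (36.0 − 33)/0.7 × 4 = 17.1 hours, which approximately 16 hours covers. From the ends of the target range the figures are 11.4 hours (34 °C) and 22.9 hours (32 °C), but 7.1 allows for variation by running the next phase from 72 hours or the end of rewarming. No change is needed.
- *That the treatment comparison is biased.* Randomisation is stratified by clinical centre, so a site's reading of eligibility applies to both of its arms, and section 7's clock does too. Nothing in the protocol shows an effect on the primary endpoint.

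**Conclusion.** The eligibility point stands: section 10.4.2 excludes severe coagulopathy, the operating lists do not, and nothing elsewhere in the protocol closes the gap. Its size cannot be stated, because the protocol gives no frequency of severe coagulopathy after arrest and does not define the term.

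The 120-hour point also stands as a contradiction, but a secondary one: a difference of 0 to 6 hours plus any start delay, at the end of temperature control. That range assumes randomisation within the six-hour limit. The start delay is left open because the protocol does not bound it.

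The probe and potassium passages are minor wording matters. Nothing here affects alpha, power or sample size. The point deserves correction because it concerns who may be cooled and what ethics boards are told, and because correction is cheap.

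**What to change.** 1. Reconcile the eligibility statement in 10.4.2 with 1.3.2 and 5.2, so that all three describe the same population. The clinical leads decide which version stands. If a coagulopathy criterion is kept, it needs a definition that a screening physician can apply.
2. State one origin for the 120-hour period in 1.4, 6.2 and section 7, and use it wherever 120 hours or the end of day 5 appears. Again the clinical leads choose.
3. As minor edits in the same amendment, either repeat the 1.0 °C notification step in 7.1 and 7.2 or otherwise reconcile it with the text there, and reconcile the potassium directive in 10.4.2 with the usual-practice statement in 7.7.

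The cost is a wording amendment, with matching changes to the manual of operations and site training. Items 2 and 3 add no patients or procedures. Item 1 adds none if 10.4.2 is brought into line with the lists. If a criterion is added to the lists instead, the leads should consider its effect on screening and accrual, which the documents do not allow us to estimate.
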